8.8 Study Drug Accountability

An accurate and current accounting of the dispensing of study drug for each participant will be maintained on an ongoing basis by a member of the study site staff. The amount of study drug dispensed will be recorded on the Investigational Drug Accountability Record. The study monitor will verify these documents throughout the course of the study.

9 STUDY PROCEDURES AND GUIDELINES

The procedures described below will be performed at the visits noted in the Schedule of Events (Appendix 1) and in Section 9.

Prior to conducting any study-related activities, written informed consent and the Health Insurance Portability and Accountability Act (HIPAA) authorization must be signed and dated by the participant or participant's legal representative. If appropriate, assent must also be obtained prior to conducting any study-related activities.

9.1 Clinical Assessments

9.1.1 Concomitant Medications

All concomitant medication and concurrent therapies will be documented as noted in the Schedule of Events. Dose, route, unit, frequency of administration, indication for administration and dates of medication will be captured.

9.1.2 Demographics

Demographic information (date of birth, sex, race) will be recorded.

9.1.3 Medical History

Relevant medical history, including history of current disease, other pertinent respiratory history, and information regarding underlying diseases will be recorded.

9.1.4 Epilepsy history

Epilepsy history will be recorded, including seizure types, proposed etiology, age of diagnosis, history of AED treatments and reasons for discontinuation/failure, history of pre-surgical investigations, history of epilepsy surgery including surgery type, date, postsurgical course, and relevant pathology.

9.1.5 Physical Examination

A complete or abbreviated physical examination will be performed by a licensed professional (MD, NP, RN, PA) as noted in the Schedule of Events. The abbreviated exam includes neurological, respiratory, cardiovascular, and abdominal assessments.

After screening, new abnormal physical exam findings must be documented as adverse events (AEs).

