For all cohorts and all grades, 25 of 26 (96%) participants experienced at least 1 treatment-related adverse event (TRAЕ). The most common nonhematologic TRAEs reported were mucosal inflammation (10 participants, 38%), fatigue (7 participants, 27%), rash (6 participants, 23%), diarrhea (6 participants, 23%), and nausea (5 participants, 19%). Most of these AEs were grade 1/2 events, with only three grade 3 nonhematologic AEs (2 elevated AST and 1 dyspnea). Specifically, at the MTD (100 mg/m²), all 7 participants experienced at least 1 TRAE of any grades, and the most common AEs were thrombocytopenia, mucositis, and fatigue (5 participants, 71% each). A total of 7 participants (27%) had infections, including candidiasis, oral candidiasis, cellulitis, folliculitis, and urinary tract infection. All these events were grade 1 or 2.

Four (15%) participants experienced at least 1 treatment-related serious AE, including cardiac arrhythmia (grade 2) and mood alteration (grade 3) both in the 125 mg/m² cohort, vomiting (grade 3) in the 45 mg/m² cohort, and dyspnea (grade 3) in the 100 mg/m² cohort.

The most common hematologic TRAE, for all cohorts and grades, were thrombocytopenia (58%), followed by hypokalemia (23%), anemia and hypophosphatemia (19% each), and neutropenia (15%). Most of these events were grade 1/2, and only one grade 4 hematologic event occurred (thrombocytopenia in the 150 mg/m² arm). At the MTD, the only hematologic AE was a grade 3 anemia.

Study PEC-001 (Malignant PEComa)

Study PEC-001 is a phase 2, multi-center, single arm, open-label, multi-institutional study to determine the efficacy and safety profile of ABI-009 administered by IV infusion in participants with malignant PEComa. The primary objective of this study is to investigate the efficacy of the mTOR inhibitor ABI-009 in advanced malignant PEComa. The secondary objectives are to further investigate the efficacy and safety of intravenous (IV) ABI-009 100 mg/m² given weekly for 2 of 3 weeks in participants with advanced malignant PEComa. At least 30 evaluable participants will be enrolled in study PEC-001.

Study PAH-001 (Severe Pulmonary Arterial Hypertension)

This study is a prospective phase 1, single arm, open-label, multi-institutional study to determine the MTD, safety, and preliminary efficacy of IV ABI-009 in participants with severe PAH. ABI-009 is administered weekly for 16 weeks with a dose range of 1-10 mg/m².

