2.1 Risk / Benefit Assessment

The mTOR inhibitors (rapamycin/sirolimus, temsirolimus and everolimus) as a class have similar side effects and safety profiles and one can refer to the package inserts of the marketed mTOR inhibitors for safety information. No new side effects were noted with ABI-009 (see investigator brochure).

The safety data available in the literature to date for all completed controlled and uncontrolled clinical studies suggest that: (a) mTOR inhibitors are generally well tolerated at both daily and weekly dose schedules, and (b) mTOR inhibitors give a favorable safety profile, with adverse events (AEs) being manageable, reversible, and non-cumulative. Most common adverse reactions (incidence $\geq 10\%$) associated with mTOR inhibitors are stomatitis, rash, fatigue, asthenia, diarrhea, anorexia, nausea, mucosal inflammation, vomiting, pneumonitis, cough, peripheral edema, infections, dry skin, epistaxis, pruritus, and dyspnea. The most common grade 3-4 adverse reactions (incidence $\geq 2\%$) were infections, stomatitis, fatigue, and pneumonitis. Non-infectious pneumonitis is a class effect of rapamycin derivatives, and some of these cases have been severe and on rare occasions, fatal outcomes have been observed.

mTOR inhibitors have immunosuppressive properties and may predispose patients to bacterial, fungal, viral or protozoan infections, including infections with opportunistic pathogens. Localized and systemic infections, including pneumonia, other bacterial infections, invasive fungal infections, such as aspergillosis or candidiasis and viral infections including reactivation of hepatitis B virus, have been described in patients taking mTOR inhibitors. Some of these infections have been severe (e.g. leading to respiratory or hepatic failure) and occasionally have had a fatal outcome.

The most common laboratory abnormalities (incidence $\geq 50\%$) associated with mTOR inhibitors are anemia, hypercholesterolemia, hypertriglyceridemia, hyperglycemia, lymphopenia, and increased creatinine. The most common grade 3-4 laboratory abnormalities (incidence $\geq 3\%$) were lymphopenia, hyperglycemia, anemia, hypophosphatemia, and hypercholesterolemia.

Comprehensive clinical safety data and nonclinical toxicology information are available for long term dosing with rapamycin and other mTOR inhibitors, which have been included in previous regulatory submissions with ABI-009 (IND 125669 and Investigator's Brochure, version 5.0).

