8.7.2 Management of stomatitis/oral mucositis/mouth ulcers

Stomatitis/oral mucositis/mouth ulcers due to mTOR inhibitors should be treated using local supportive care. Please note that investigators in earlier trials have described the oral toxicities associated with mTOR inhibitors as mouth ulcers, rather than mucositis or stomatitis. If your examination reveals mouth ulcers rather than a more general inflammation of the mouth, please classify the adverse event as such. Please follow the paradigm below for treatment of stomatitis/oral mucositis/mouth ulcers:

1. For mild toxicity (Grade 1), conservative measures such as non-alcoholic mouth wash or salt water (0.9%) mouthwash several times a day until resolution is recommended
2. For more severe toxicity (Grade 2 in which case participants have pain but are able to maintain adequate oral alimentation, or Grade 3 in which case participants cannot maintain adequate oral alimentation), the suggested treatments are topical analgesic mouth treatments (i.e., local anesthetics such as benzocaine, butyl aminobenzoate, tetracaine hydrochloride, menthol, or

phenol) with or without topical corticosteroids, such as triamcinolone oral paste 0.1% (Kenalog in Orabase®).

3. Agents containing hydrogen peroxide, iodine, and thyme derivatives may tend to worsen mouth ulcers. It is preferable to avoid these agents.

4. Antifungal agents must be avoided unless a fungal infection is diagnosed. In particular, systemic imidazole antifungal agents (ketoconazole, fluconazole, itraconazole, etc.) should be avoided in all participants due to their strong inhibition of mTOR inhibitor metabolism, thereby leading to higher mTOR inhibitor exposures. Therefore, topical antifungal agents are preferred if an infection is diagnosed. Similarly, antiviral agents such as acyclovir should be avoided unless a viral infection is diagnosed.

Note: Stomatitis/oral mucositis should be appropriately graded using the functional grading given on the NCI-CTCAE for adverse events, v5.

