10 EVALUATIONS BY VISIT

10.1 Screening Assessments (Day -14 to 0)

1. Review the study with the participant (participant's legal representative) and obtain written informed consent and HIPAA authorization and assent, if appropriate.
2. Review eligibility (including epilepsy history)
3. Perform extended physical examination
4. Record demographics data
5. Record medical history, including a history of epilepsy, diagnosis date, and prior epilepsy treatments.
6. Vital signs (Height, pulse, blood pressure, respiration rate, temperature and weight)
7. Current medications and baseline conditions
8. Neurologic exam
9. Pulse oximetry (must be >93)
10. Laboratory assessments as required per the schedule of evaluations (need to be from within the last 30 days)
 - a. Complete Blood Count (CBC) with differential and platelet count
 - b. Blood chemistry assessment, including:
 - i. Sodium, potassium, chloride, bicarbonate, calcium, fasting glucose, albumin
 - ii. Total protein, BUN, serum creatinine
 - iii. Total bilirubin, AST, ALT, alkaline phosphatase, uric acid, phosphorus
 - iv. Fasting serum lipid profile (total cholesterol, triglycerides, HDL and LDL)
 - c. Coagulation assessment, including prothrombin time, partial thromboplastin time, international normalized ratio (PT/PTT/INR)

- d. Hepatitis B and C screening. Hepatitis B screening can be deferred in participants who have a history of having received the entire Hepatitis B immunization series and documentation is provided.
- e. Serum or urine pregnancy test: If participant is of child-bearing potential, pregnancy test should be done at screening and monthly thereafter. If urine test is positive, confirmatory blood testing will be performed.
- f. HIV seropositivity screening, if necessary.

11. If available and consent to archive has been given: Archival brain tissue tumor samples from a prior surgery will be used to test for molecular analyses. An email from the pathology/genetics department(s) may be used to confirm tissue availability at the time of enrollment.

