10.5 Visit 6: Post-Dosing One-Week Assessment (+/-2 days)

1. Review adverse events.
2. Review epilepsy diary.

3. Investigator opinion regarding seizures recorded: same, worse, somewhat better, better.
4. Record changes to concomitant medications.
5. Perform abbreviated physical examination.
6. Obtain and record vital signs.
7. Collect urine for pregnancy test (if child-bearing potential).
 - a. If positive confirm with blood test
8. Collect blood for clinical laboratory tests (chemistry, hematology).
9. Laboratory assessments as required per the schedule of evaluations
 - c. Complete Blood Count (CBC) with differential and platelet count
 - d. Blood chemistry assessment, including:
 - i. Sodium, potassium, chloride, bicarbonate, calcium, fasting glucose, albumin,
 - ii. Total protein, BUN, serum creatinine.
 - iii. Total bilirubin, AST, ALT, alkaline phosphatase, uric acid, phosphorus,
 - iv. Fasting serum lipid profile (total cholesterol, triglycerides, HDL and LDL)
10. Coagulation assessment, including prothrombin time, partial thromboplastin time, international normalized ratio (PT/PTT/INR)
11. Whole blood rapamycin trough level
12. Administer C-SSRS, QOLCE, and NCBRF

10.6 Follow-up Visits 7, 8, & 9: 30, 60, and 90 Days Post-Dosing (+/-7 days)

1. Review participant diary for compliance and seizure frequency.
2. Safety follow-up labs at Visit 7 per PI discretion following Visit 6 labs.
3. Investigator opinion regarding seizures recorded: same, worse, somewhat better, better
4. Record changes to concomitant medications.
5. Perform abbreviated physical exam (30 days post-doing only).
6. Measure and record height and weight (at final study visit).
7. Obtain and record vital signs (30 days post-dosing only).
8. On final visit (90 days post-dosing) administer C-SSRS, QOLCE and NCBRF

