APPENDIX 1. SCHEDULE OF EVENTS

	SCREENING DAY -14 TO DAY 0*	VISIT 1: DAY 0	VISIT 2: DAY 30**	VISIT 3: DOSE 1	VISITS 4&5: DOSES 2 AND 3	VISIT 6: ONE WEEK POST- DOSING	VISITS 7&8: 30 AND 60 DAYS POST-DOSING	VISIT 9: 90 DAYS POST- DOSING	EARLY PERMANENT DISCONTINUATION
Informed Consent Process	X								
Enrollment Eligibility Checklist	X								
Demographics	X								
Extended Physical Exam	X								
Neurological Exam	X								
Hepatitis C, and Hepatitis B, HIV if necessary ^A	X								
Epilepsy and Medical History	X								
Height, Weight, and BSA	X			X				X	X
Vitals	X		X	X	X	X			
Pulse Oximetry ^F	X		X	X	X				
CBC with Differential ^C	X		X	X	X	X	X ^B (visit 7 only)		X
Serum Chemistries with Coagulation Assessment ^E	X		X	X	X ^B (visit 4 required)	X ^B	X ^B (visit 7 only)		X
Urine Pregnancy ^G	X		X						
Study Continuation Checklist			X	X	X	X	X		
Abbreviated Physical Exam		X	X	X	X	X	X ^D		X
Concomitant Medication Review		X	X	X	X	X	X	X	X
Dispense Seizure Diary and Glossary		X							
Administer QOLCE, NCBRF, & C-SSRS			X			X		X	X
Review Seizure Diary			X	X	X	X	X		X
Investigator Opinion			X	X	X	X	X		
Dosing Checklist				X	X				
Study Drug Administration				X	X				
Adverse Events			X	X	X	X	X	X	X
Whole Blood Rapamycin Level ^H					X	X			X

*Screening may be combined with Visit 1

**Visit 2 may also be Visit 3 Dose 1

^A Hepatitis C (and if necessary, Hepatitis B) test: 2 mL SST gold top tube. HIV seropositivity test, if necessary: 2 mL gold top tube. If testing for all together, can use one 4 mL SST gold top tube.

^B Only if previous chemistries or coagulation profiles are abnormal or are otherwise clinically indicated.

^C CBC with differential: 1 mL EDTA lavender top tubes if testing with blood trough rapamycin levels. If testing alone can collect only 0.5 mL in EDTA tube.

^D Only at 30 days post-treatment

^E 2 x 4 mL SST gold top tubes. Serum chemistry: Na, K, Cl, CO₂, Ca, fasting glucose, BUN, creatinine, total protein, albumin, total bilirubin, aspartate aminotransferase (AST/SGOT), alanine aminotransferase (ALT/SGPT), alkaline phosphatase, uric acid, Ph, fasting serum lipid profile. Coagulation assessment: 1.8 mL Sodium Citrate light blue top tubes. Coagulation assessment including prothrombin time, partial thromboplastin time, international normalized ratio (PT/PTT/INR).

^F Must be greater than 93% on room air to continue with study procedures

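### No scheduled exam after screening explicitly requires inspection of the mouth or skin, although stomatitis/mucositis and rash are among the most expected toxicities

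*Combined protocol and SAP*

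**What the plan says.** Section 9.1.5 allows a complete or an abbreviated physical exam and describes only the second: "The abbreviated exam includes neurological, respiratory, cardiovascular, and abdominal assessments". It also requires any new abnormal finding after screening to be recorded as an adverse event, so the exam is a formal route into adverse-event incidence, a primary endpoint in Section 5.1.

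The fuller exam appears once. Section 10.1 has "Perform extended physical examination" at screening, and the row "Extended Physical Exam" in Appendix 1 is marked only in the screening column. Later visits call for the short form; at Visit 6, for example, Section 10.5 says "Perform abbreviated physical examination".

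On expected toxicity, Section 2.1 says that the most common adverse reactions "associated with mTOR inhibitors are stomatitis, rash, fatigue", and the list goes on from there. Section 8.7.2 tells staff: "If your examination reveals mouth ulcers rather than a more general inflammation of the mouth, please classify the adverse event as such".

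**The concern.** Section 8.7.2 assumes that someone looks in the mouth, but the exam defined in Section 9.1.5 does not ask for it at any visit after screening. The same holds for the skin. These are two of the places where this drug's toxicity is most likely to be visible.

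Without a required inspection, a painless ulcer or a faint rash is recorded only if the examiner happens to look, or if the participant or family notices it and says so when asked or in the diary. Participants may be as young as 3, and Section 1.1 describes frequent intellectual impairment in uncontrolled childhood epilepsy, so some cannot describe a lesion well. Detection could also vary between examiners, who may be physicians, nurse practitioners, nurses or physician assistants.

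At stake is the completeness of low-grade counts in the adverse-event tables of Section 15.3 and in the summaries that Section 14 sends to the DSMB before each escalation and before the MTD expansion.

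**Working it through.** **1. Exams by visit (Section 10, checked against Appendix 1).**
- Screening: extended.
- Visits 1, 2, 3, 4, 5 and 6: abbreviated.
- Visit 7 (30 days after dosing): abbreviated.
- Visits 8 and 9 (60 and 90 days): none.
- Early discontinuation: abbreviated.

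So every exam from Visit 1 on is the four-system one. The content of the extended exam is not listed; that it covers mouth and skin is a reasonable reading, not a stated fact.

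**2. Expected toxicities, reproduced from the plan's counts.**
- Mucosal inflammation, earlier ABI-009 phase 1 study (Section 1.11): 10/26 = 38.5%, stated as 38%.
- Rash, same study: 6/26 = 23.1%, stated as 23%.
- Oral ulcer, paediatric rapamycin study (Section 1.7): 12/52 = 23.08%, as stated, and described there as the main side effect.

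The first study used 45 to 150 mg/m²; this trial uses 1 to 20 mg/m² for three doses, so its rates may not carry over. The second is closer in exposure. Its blood levels averaged 6.5 µg/L (6.5 ng/mL), against predicted weekly troughs here of 3.56 ng/mL at 5 mg/m² to 14.22 ng/mL at 20 mg/m² (Table 1). That comparison is loose, because Section 1.7 is unsure that its levels are troughs and treatment there lasted at least 24 weeks. It supports expecting oral lesions, but it does not give a rate.

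**3. Other routes into the adverse-event record.**
- Section 11.1: the investigator asks about events at each visit.
- Section 9.1.11: a mandatory daily diary records new symptoms, completed by participants and parents or guardians.
- Section 16.1: parents submit the diary electronically each day.

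These are active routes, but each needs someone to have noticed the lesion.

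**4. Grades exposed.** Section 8.7.2 grades oral toxicity by function: grade 2 means pain with adequate intake, grade 3 means intake fails. Both are symptoms that questions and a diary should find. That leaves chiefly grade 1 oral lesions and mild rash. Section 8.5 requires grade 3 or higher for a DLT, so the exposed events do not count towards escalation.

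**5. Age of the last full exam when dosing starts.** Screening falls on Day -14 to 0 and Visit 2 on Day 30 (+5/-2); Appendix 1 lets Visit 2 serve as the dose 1 visit.
- Shortest gap: 30 − 2 − 0 = 28 days.
- Longest gap to Visit 2: 30 + 5 + 14 = 49 days.

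The last exam that can be presumed to cover mouth and skin is therefore four to seven weeks old at Visit 2. Section 15.3 counts events that arise after dosing begins, so a recent pre-dose state is needed to call a finding new.

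**6. Why no undercount is computed.** Recorded rate = true rate × fraction detected. The documents give neither factor for this trial: the true rate at these doses is unknown, and nothing states what fraction questioning and diary would find.

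**The case against.** The strongest reply is that the protocol does not exclude the inspection. Section 9.1.5 uses a word that leaves its list open, Section 8.7.2 presupposes an oral look at least where a lesion is suspected, and any finding made must be recorded. Events are also sought at every visit and through a daily diary that parents submit. All of that stands, and it limits the point to what is required, not to what may happen in practice.

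A reader might infer more in four ways, none of which the documents support:
- *That these toxicities count only if someone volunteers them.* Questioning is scheduled, parents share the diary, and participants range from 3 to 26 years.
- *That moderate or severe events are missed, or that the MTD is at risk.* Grades 2 and 3 of oral toxicity are defined by pain or failed intake, and escalation depends on grade 3 or higher.
- *That the undercount can be sized by applying 38% and 23% to 18 participants with an assumed detection fraction.* Those rates come from an oncology study at higher doses. How that study found its events is not stated, and mucosal inflammation is listed separately from stomatitis in Section 2.1.
- *That there is no pre-dose state at all.* The extended exam is done at screening, and baseline adverse events are collected at Visit 2. What is missing is a required re-check of mouth and skin close to dose 1.

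The separate labels for ulcers and stomatitis are a deliberate instruction. Section 15.3 already groups events by body system and System Organ Class, so no change is asked for there.

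**Conclusion.** The gap is real and modest. After screening, no scheduled exam explicitly requires a look at the mouth or skin, and Sections 9.1.5 and 8.7.2 do not fit together. Low-grade oral lesions (chiefly grade 1) and mild rash may be undercounted in the primary adverse-event endpoint and in the DSMB summaries, by an amount the documents do not allow to be estimated. The effect on DLTs and the MTD is probably small.

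This rests on two assumptions: that staff follow the four-system list as written, and that some low-grade lesions go unnoticed or unmentioned by participants and families. The point is worth acting on because the correction is cheap and falls on toxicities the protocol itself expects.

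**What to change.** In Section 9.1.5, add oral mucosa and skin to the systems in the abbreviated exam, so that it agrees with Section 8.7.2, and give each a field on the exam form. The definition then applies wherever that exam is already scheduled:
- at Visit 2, or at Visit 3 before dose 1 (Section 10.4 lists the exam ahead of drug administration), as the pre-dose comparator;
- at the later visits through Visit 7;
- at early discontinuation.

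No visit or sample is added. The cost is roughly a minute per exam (an estimate), so about 7 minutes per participant over the exams at Visits 1 to 7 (7 × 1). More low-grade adverse events will be recorded, which should be borne in mind when rates are set beside studies that did not inspect routinely. The change concerns data capture only and leaves dosing and clinical management as they are.

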9.1.6 Weight and Height

Weight will be measured on the same scale and recorded as noted in the Schedule of Events. Adults and children may remain in clothes (without shoes). A standing height will be measured and recorded as noted in the Schedule of Events.

